## Statistical Analysis Plan

Sponsor Name: Golden Biotechnology Corporation  
Sponsor Protocol ID: GH Covid-2-001

Covance Study ID: 000000203201

For hematology, clinical chemistry and numerical urinalysis analytes, shift tables presenting movement in and out of reference range from baseline to each scheduled post-baseline visit will be provided for each treatment group and overall for the SS.

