4.2. Exclusion Criteria

Patients will be excluded from the study if they satisfy any of the following criteria at the screening visit unless otherwise stated:

1. Female patient is pregnant or breastfeeding.
2. Any patient's concomitant life-threatening condition, including but not limited to: requiring mechanical ventilation, acute respiratory distress syndrome, shock, or cardiac failure.
3. Evidence of multi-lober consolidation pneumonia or cavities on chest x-ray or CT scan.
4. Severe COVID-19 disease as defined by the WHO COVID-19 Clinical Improvement Ordinal Scale, scores of 5 (non-invasive ventilation or high-flow oxygen), 6 (intubation and mechanical ventilation), or 7 (ventilation + additional organ support-pressors, renal replacement therapy, ECMO).
5. Medical history significant for the following pulmonary diseases: lung cancer, cystic fibrosis, empyema.
6. Respiratory rate >30 respirations per minute.
7. History of abuse of drugs or alcohol that could interfere with adherence to study requirements as judged by the investigator.
8. Treatment with other drugs thought to possibly have activity against COVID-19 within 7 days prior to enrollment or concurrently. Note: remdesivir or other authorized treatments for COVID-19 is allowed if considered SoC, if started prior to randomization or during the study.
9. Use of *A. camphorata*-containing products within 2 weeks prior to the first administration of study drug.
10. Use of other investigational drugs within 30 days of dosing, or plans to enroll in another clinical trial of an investigational agent while participating in the present study.
Note: authorized COVID-19 vaccines are not considered investigational and are not exclusionary.
11. Clinically significant abnormal ECG at screening, as determined by the investigator.
12. Patient requires frequent or prolonged use of systemic corticosteroids (≥ 20 mg of prednisone/day or equivalent for >4 weeks) or other immunosuppressive drugs (eg, for organ transplantation or autoimmune conditions).
13. Abnormal laboratory values at screening:
 - a. Estimated glomerular filtration rate <50 mL/min.
 - b. Alanine aminotransferase (ALT) or aspartate aminotransferase (AST) $>5 \times$ upper limit of normal (ULN), or ALT/AST $>3 \times$ ULN plus total bilirubin $>2 \times$ ULN.
 - c. Total bilirubin $>1.5 \times$ ULN, unless the patient has known Gilbert's syndrome.
 - d. Hemoglobin <9 g/dL for females or <11 g/dL for males.

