4.4.2. Hepatic injury or renal impairment

4.4.2.1. *Hepatic injury*

Discontinuation of study treatment for abnormal liver tests should be considered by the investigator when a patient meets one of the conditions outlined in [Figure 2](#) or if the investigator believes that it is in the best interest of the patient.

Figure 2: Stopping Criteria for Liver Injury

Abbreviations: ALT = alanine aminotransferase; INR = international normalized ratio; ULN = upper limit of normal
 Note: INR value is not applicable to patients on anticoagulants.

4.4.2.2. *Renal impairment*

If a patient has renal impairment (creatinine clearance <50 mL/min), treatment should be discontinued.

4.4.3. **Discontinuation of study treatment**

A patient may be discontinued early from study drug treatment (ET of study treatment) for the following reasons:

- Lack of efficacy (e.g. patients who require nonstudy antiviral or anticytokine therapy due to progression of COVID-19), and the investigator's decision. Note: remdesivir or other authorized treatments for COVID-19 is allowed if considered SoC, if started prior to randomization or during the study. Initiation of remdesivir or other authorized treatments for COVID-19 during the study will be considered a treatment failure if started due to progression of disease.
- Adverse event
- Withdrawal by patient (specify reason in the eCRF)
- Lost to follow-up
- Death

- Physician decision (i.e. investigator decision based on protocol deviation, assessment that it is not in the patient's best interest to continue, or other reason [specify reason in the eCRF]).
- Sponsor decision (specify reason in the electronic case report form [eCRF])

No temporary treatment discontinuation is permitted.

Patients who discontinue study treatment prematurely will be asked about the reason(s) for discontinuation and will be asked to continue all assessments up to Day 28. Patients will be educated about the continued scientific importance of their data and encouraged to complete the Day 28 Follow-up/EOS assessments even if they discontinue study treatment prematurely.

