7.2.3. Clinical laboratory evaluations

Blood and urine samples will be collected for clinical laboratory evaluations at the times indicated in the Schedule of Assessments in [Appendix 5](#). Clinical laboratory evaluations are listed in [Appendix 2](#). Additional clinical laboratory evaluations will be performed at other times

if judged to be clinically appropriate or if the ongoing review of the data suggests a more detailed assessment of clinical laboratory safety evaluations is required.

Serum pregnancy test is to be performed in female patients of child bearing potential at a local (site) laboratory, during screening or Day 1, discharge, and ET/EOT. A urine pregnancy test may be performed but must be confirmed with a serum pregnancy test (screening only). The Follow-up/EOS visit test will be a urine pregnancy test only (no serum pregnancy test confirmation). Additionally, local/country regulations will be followed as applicable (eg., a pregnancy test one month following the last dose of study treatment in female patients of childbearing potential).

Screening laboratory test will be assessed by a local laboratory, and baseline and postbaseline laboratory tests will be assessed by a central laboratory. If delays in transportation of the samples are encountered, then local safety laboratory samples can be obtained instead for samples that can't be frozen for shipment (e.g. hematology and urine). Baseline laboratory tests can be done once patients eligibility is confirmed. The investigator will perform a clinical assessment of all clinical laboratory data.

All screening laboratory results must be available and reviewed before the patient receives the first dose of study treatment on Day 1. After the test results are evaluated, the investigator should judge whether the patient is still eligible to stay in the study. Significant abnormal values occurring during the study will be followed until repeat test results return to normal, stabilize, or are no longer clinically significant.

In this study, clinical laboratory tests will be performed predose on Days 1, 5, and 14 (+2 days).

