## Statistical Analysis Plan

Sponsor Name: Golden Biotechnology Corporation  
 Sponsor Protocol ID: GH Covid-2-001

Covance Study ID: 000000203201

Principle	Value
Treatment group labels and order	Antroquinonol 100 mg BID Placebo
Tables	Data in summary tables presented by treatment group, assessment and visit (where applicable).
Listings	All data collected presented by treatment group, country, site, Patient, assessment and visit (where applicable), unless otherwise specified.
Descriptive summary statistics for continuous variables	Number of patients/observations (n), mean, standard deviation (SD), median, minimum (Min) and maximum (Max).
Descriptive summary statistics for categorical variables	Frequency counts and percentages [n (%)]
Denominator and for percentages	Number of patients in the analysis population, unless stated otherwise in table shell(s).
Precision for percentages	1 decimal place
Include "Missing" as category	Yes, when the number missing is greater than zero for at least one treatment group.
Display to one more decimal place than collected value	For efficacy and safety: Mean Mean Difference Median
Display to two more decimal places than collected value	For efficacy and safety: Standard Error Standard Deviation Confidence Interval
Display to three significant figures	For PK: Mean Standard Deviation Geometric Mean Median Min Max
Limit of precision for displays	4 decimal places
Date Format	DDMMYYYY

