### 7.7.3 Laboratory Evaluations

Data for the following hematology, clinical chemistry, and urinalysis analytes will be listed and summarized by treatment group and overall by visit for the SS. If data for any additional analytes are also received/recorded then these will be listed only.

Hematology	Clinical Chemistry	Urinalysis
Hematocrit	Albumin	Color and appearance
Hemoglobin	ALP	pH and specific gravity
MCH	ALT	Bilirubin
MCHC	AST	Glucose
MCV	BUN	Ketones
Platelet count	Calcium	Leukocytes
Red blood cell (RBC) count	Chloride	Nitrite
White blood cell (WBC) count	Cholesterol	Occult blood
WBC differential (% and absolute values):	Creatinine	Protein
• Basophils	GGT	Microscopic (including RBCs and WBCs)
• Eosinophils	Glucose	
• Lymphocytes	eGFR	
• Monocytes	LDH	
• Neutrophils	Phosphorus	
	Potassium	
	Sodium	
	Total Bilirubin	
	Total CO 2 (measured as bicarbonate)	
	Total Protein	
	Triglycerides	
	Uric acid	

Abbreviations: ALP = alkaline phosphatase; ALT = alanine aminotransferase; AST = aspartate aminotransferase; BUN = blood urea nitrogen; CBC = complete blood count; CO2 = carbon dioxide; eGFR = estimated glomerular filtration rate; GGT = gamma glutamyl transferase; LDH = lactate dehydrogenase; MCH = mean corpuscular hemoglobin; MCHC = mean corpuscular hemoglobin concentration; MCV = mean corpuscular volume; RBC = red blood cell; WBC = white blood cell.

All laboratory data will be reported in International System of Units (SI). Out-of-reference-range values will be flagged as high (H) or low (L) in the listings.

For analysis purposes, values preceded by a "<" or a ">" sign (i.e. those below or above the limits of quantification) will be multiplied by 0.5 and 1.5 respectively.

Results and changes from baseline (if applicable) of all laboratory parameters will be listed and summarized by treatment group and overall, for each scheduled visit using standard descriptive statistics for the SS.

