### 7.7.5 Electrocardiograms

The following quantitative ECG measurements will be taken during the study:

- heart rate (bpm);
- RR interval (msec);
- PR interval (msec);
- QRS interval (msec);
- QT interval (msec);
- Bazett corrected QT (QTcB) interval (msec);
- Fridericia corrected QT (QTcF) interval (msec).

An overall Investigator assessment of ECG will be provided (categories "normal", "abnormal, not clinically significant" and "abnormal, clinically significant").

The ECG measurements and changes from baseline in ECG will be listed and summarized by treatment group and overall for each scheduled visit using standard descriptive statistics for the SS.

The Investigator assessment will be listed and the number and percentage of patients within each assessment category will be tabulated by treatment group and overall for each scheduled visit for the SS. Shifts from baseline in overall investigator assessment at each post-baseline visit will be presented.

QTcB and QTcF intervals and change from baseline will be analyzed. The analysis will include all scheduled and unscheduled values.

The maximum baseline and post-baseline values will be summarized separately, by treatment group and overall according to the following categories:

- ≤450 ms
- >450 and ≤480 ms

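### No planned laboratory table counts, per arm, patients whose liver tests worsen from an already raised baseline, although entry allows ALT/AST up to 5 x ULN

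*SAP*

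**What the plan says.** **Entry.** Protocol 4.2, criterion 13b, excludes on transaminases only at "aspartate aminotransferase (AST) $>5 \times$ upper limit of normal (ULN"), or above 3 x ULN when total bilirubin is also above 2 x ULN. Criterion 13c excludes at "Total bilirubin $>1.5 \times$ ULN", with an exception for known Gilbert's syndrome. Raised values below these limits are therefore allowed at baseline.

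**Laboratory outputs.** SAP 7.7.3 has two kinds of table:
- Categorical: "shift tables presenting movement in and out of reference range from baseline to each scheduled post-baseline visit will be provided".
- Continuous: "Results and changes from baseline (if applicable) of all laboratory parameters will be listed and summarized by treatment group and overall", by scheduled visit. SAP 7.1 defines the statistics as "Number of patients/observations (n), mean, standard deviation (SD), median, minimum (Min) and maximum (Max").

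The listings flag values only as high or low.

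**Unscheduled values.** Protocol 7.2.3 foresees repeat tests: "Significant abnormal values occurring during the study will be followed until repeat test results return to normal, stabilize". In the by-visit analyses, SAP 6.1 lets a scheduled visit take precedence over an unscheduled one in the same window. An unscheduled visit is used only if its window holds no scheduled visit.

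**Liver conditions.** Protocol 4.4.2.1 says "Discontinuation of study treatment for abnormal liver tests should be considered by the investigator" when a condition in Figure 2 is met. The SAP has no count of patients who meet one.

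**QTc, for contrast.** SAP 7.7.5 tabulates maximum values and maximum increases in threshold categories. It adds: "The analysis will include all scheduled and unscheduled values".

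**The concern.** An in/out-of-range table shows patients leaving the normal range. It cannot show worsening in a patient who starts outside it, and this trial deliberately admits such patients. Safety is a stated secondary objective, and Protocol 1.3 says that the drug's safety has not been assessed in this population. A reader of the final report would want to know how many patients in each arm went from moderately raised to markedly raised enzymes, and whether any had transaminases and bilirubin raised together. The SAP already uses threshold categories and worst values for QTc. It does not do so for the liver, for which the protocol has its own discontinuation section.

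**Working it through.** The plan states no figure on this point, so there is nothing to reproduce. The check applies the planned classification to example courses, sizes the group affected, and traces which samples reach the tables.

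**1. Classification.** A value is high if it exceeds 1 x ULN. The courses below are illustrative, and every baseline is within the entry limits. The last column uses the bands proposed in the fix.

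| Analyte | Baseline to post-baseline (x ULN) | Planned table | Proposed bands |
|---|---|---|---|
| ALT | 0.8 to 1.2 | normal to high | <=1 to >1-3 |
| ALT | 1.5 to 4 | high to high | >1-3 to >3-5 |
| ALT | 2 to 10 | high to high | >1-3 to >5-10 |
| ALT | 4 to 12 | high to high | >3-5 to >10 |
| ALT | 4.9 to 20 | high to high | >3-5 to >10 |
| ALT | 4.9 to 1.1 | high to high | >3-5 to >1-3 |
| Bilirubin | 1.4 to 3.0 | high to high | >1-2 to >2 |

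The planned table counts the first row, a trivial rise, as a shift. It puts the next four rows and the improvement from 4.9 to 1.1 in one cell. The proposed bands separate worsening from improvement.

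**2. How many patients.** The planned size is 174 randomized 1:1, so 174 / 2 = 87 per arm. The documents do not give the share entering with a given analyte above range, so I assume a range:
- 10%: 0.10 x 87 = 8.7, about 9 per arm
- 50%: 0.50 x 87 = 43.5, about 44 per arm

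These patients cannot register an upward shift for that analyte in that table. A patient with high ALT but normal AST and bilirubin can still register a shift in the other two.

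**3. What the continuous summary shows.** If k of 87 patients rise from 4 to 12 x ULN and the rest do not change, the mean change is k x 8 / 87:
- k = 1: 8 / 87 = 0.09 x ULN
- k = 3: 24 / 87 = 0.28 x ULN

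The mean hardly moves. The maximum change does show the full 8 x ULN if the sample is at an analysed visit, but it is the same for k = 1 and k = 3.

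**4. Which samples reach the tables.** The SAP 6.1 windows are Days 2-3, 4-6, 7-8, 14-16 and 26-30. Days 9-13 and 17-25 lie in no window. Laboratory tests are scheduled on Days 1, 5 and 14 and at the discharge/early-termination visit, for which the window table has no row. An unscheduled peak reaches only the listings if it shares a window with a scheduled visit or falls outside every window. It can be used if its window has no scheduled visit.

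**5. Joint pattern.** ALT, AST and bilirubin are summarized separately. No table links them within a patient.

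**The case against.** The case on the other side is substantial. The word invisible, which a reader might be tempted to use, is not supported:
- Results and changes are summarized with minimum and maximum, so a large rise at an analysed visit will normally appear as the maximum for its arm.
- Every value is listed.
- Protocol Appendix 1 makes a laboratory abnormality an adverse event if it brings symptoms, needs intervention or changes study treatment. A patient taken off drug for liver tests would fit that and appear in the tables of events causing discontinuation.
- An independent DMC reviews safety throughout.
- Protocol 8.5 promises only descriptive summaries, with shift tables where applicable, and the SAP delivers that.

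All of this stands, and it limits the point. It does not close the gap. A maximum is one number per arm and visit, not a count. The high/low flag is the same at 1.1 and 12 x ULN. Appendix 1 also exempts abnormal laboratory findings associated with the underlying disease unless the investigator judges them more severe than expected, so a rise attributed to COVID-19 may never become an adverse event. DMC review during the trial does not supply a table for the final report.

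Three further inferences should not be drawn:
- That patients with raised baselines contribute no information on worsening. They contribute to the change summaries, listings and adverse-event data.
- That a patient could meet the liver discontinuation conditions and leave no trace. The thresholds in Figure 2 are not reproduced in the text available, and the wording asks the investigator to consider discontinuation.
- That the trial will restate the absence of hepatotoxicity from this table. The sentence in Protocol 1.3 refers to previous studies, and the SAP plans no such claim.

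**Conclusion.** The point holds as a gap in tabulation. No planned output counts, per arm, patients whose ALT, AST or bilirubin worsens from a raised baseline, or who have ALT/AST and bilirubin raised together. Some unscheduled peaks reach only the listings.

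The size cannot be fixed from the documents. The range of about 9 to 44 per arm rests entirely on the assumed 10% to 50% share and on the planned 87 per arm. It applies per analyte and to the shift table only. The mean-change figures also assume that all 87 have data and that the other patients do not change. The finding that the table has this limit rests on the entry criteria and SAP 7.7.3 alone.

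The primary analysis and the error rate are not affected. This is a cheap and worthwhile improvement to safety reporting.

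**What to change.** In SAP 7.7.3, following the QTc approach in SAP 7.7.5, add by treatment group for the Safety Set:
1. A shift table for ALT, AST and total bilirubin in multiples of ULN, from baseline to the worst post-baseline value, using all scheduled and unscheduled results whatever their visit window. Possible bands are <=1, >1-3, >3-5, >5-10 and >10 for ALT and AST, and <=1, >1-2 and >2 for bilirubin.
2. A count of patients with post-baseline ALT or AST >3 x ULN together with total bilirubin >2 x ULN, the pairing already used in exclusion 13b. State whether both values must come from the same sample.

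Add a footnote that unscheduled sampling may differ between arms, so an arm sampled more often has more chances to show a high worst value.

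The cost is one or two descriptive tables from data already collected. A rise within one band would still not count as a shift, but the maximum change remains available for that. No visit, sample, test of significance or clinical discontinuation condition changes.

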### 7.7.4 Vital Signs

The following vital sign parameters will be listed and summarized by treatment group and overall and visit.

- systolic and diastolic blood pressure (mmHg);
- pulse rate (bpm);
- respiration rate (breaths/min);
- body temperature (°C).

Vital signs data and changes from baseline in vital signs will be listed and summarized by treatment group and overall, for each scheduled visit using standard descriptive statistics for the SS.

### 7.7.5 Electrocardiograms

The following quantitative ECG measurements will be taken during the study:

- heart rate (bpm);
- RR interval (msec);
- PR interval (msec);
- QRS interval (msec);
- QT interval (msec);
- Bazett corrected QT (QTcB) interval (msec);
- Fridericia corrected QT (QTcF) interval (msec).

An overall Investigator assessment of ECG will be provided (categories "normal", "abnormal, not clinically significant" and "abnormal, clinically significant").

The ECG measurements and changes from baseline in ECG will be listed and summarized by treatment group and overall for each scheduled visit using standard descriptive statistics for the SS.

The Investigator assessment will be listed and the number and percentage of patients within each assessment category will be tabulated by treatment group and overall for each scheduled visit for the SS. Shifts from baseline in overall investigator assessment at each post-baseline visit will be presented.

QTcB and QTcF intervals and change from baseline will be analyzed. The analysis will include all scheduled and unscheduled values.

The maximum baseline and post-baseline values will be summarized separately, by treatment group and overall according to the following categories:

- ≤450 ms
- >450 and ≤480 ms

## Statistical Analysis Plan

Sponsor Name: Golden Biotechnology Corporation  
Sponsor Protocol ID: GH Covid-2-001

Covance Study ID: 000000203201

- >480 and ≤500 ms
- >500 ms

The maximum increases from baseline will be summarized by treatment group and overall according to the following categories:

- ≤30 ms
- >30 and ≤60 ms
- >60 ms

### 7.7.6 Physical Examination

Physical examination results (categories “normal”, “abnormal, not clinically significant” and “abnormal, clinically significant”) and details of abnormalities will be listed for each patient.

For each physical examination body system, shifts from baseline in examination results at each post-baseline visit will be presented by treatment group and overall for the SS.

### 7.7.7 Chest Imaging

Chest imaging (X-Ray or CT scan) results (categories “normal”, “abnormal, not clinically significant” and “abnormal, clinically significant”) and other details will be listed for each patient. Shift from baseline in results at each post-baseline visit will be presented by treatment group and overall for the SS.

### 7.7.8 Oxygenation

Oxygenation parameters (i.e., FiO2, SpO2, PaO2, SpO2/FiO2 and PaO2/FiO2, if available) and other details will be listed for each patient. Change from baseline of SpO2, SpO2/FiO2 and PaO2/FiO2, at each post-baseline visit will be presented by treatment group and overall for the SS, if available.

### 7.7.9 Other Safety Variables

Other safety variables and corresponding data, if collected, will be listed only.

## 7.8 Pharmacokinetics

### 7.8.1 General

The PK parameters of antroquinonol will be calculated based on the actual sampling time using non-compartmental analysis (NCA) methods within Phoenix WinNonlin Version 8.1 or higher (Certara USA, Inc.). If the actual sampling time is missing, the scheduled timepoint will be used in the PK parameter calculation with sponsor approval.

The units of concentration and resulting PK parameters, will be presented as they are received from the analytical laboratory.

The following PK parameters for antroquinonol will be determined where possible from the plasma concentration data collected on Day 3:

